2. STATISTICAL ANALYSIS PLAN AND STATISTICAL REPORTS

This document provides the details of the statistical analyses planned for the trial. Prior to locking the database and breaking the code, this Statistical Analysis Plan (SAP) will be updated. The final SAP will define all “pre-specified, pre-planned analyses” and will trump the protocol.

3. SYNOPSIS OF THE STUDY

A Randomized, Single-Center, Double-Blind, sham-controlled, Efficacy Study of tDCS combined with SALT for stroke-induced aphasia patients.

4. STUDY DESIGN AND OBJECTIVES

Subjects will be randomized 1:1 to A-tDCS or S-tDCS, with the goal of having 50 randomized subjects for whom the PNT was collected at 1 week post-treatment. This study design will allow us to assess whether A-tDCS over targeted region coupled with computer-delivered SALT is associated with greater gains in accuracy in naming pictures, compared to sham combined with the same computer-delivered SALT in post stroke aphasia.

The primary objective of the study is to determine whether A-tDCS coupled with SALT will improve naming performance of participants with post stroke aphasia more effectively than SALT alone (i.e., the sham condition).

Planned enrollment duration: approximately 4 years (1.04 patients /month)

Duration of treatment phase: 3 weeks

Duration of follow-up in post-treatment Phase: 20 week post treatment (i.e. 23 weeks from baseline)

5. DEFINITION OF TARGET POPULATION

5.1 Target Population

Patients with aphasia diagnosis who experienced an acute ischemic, left hemisphere stroke within 90 days.

5.2 Modified Intent-to-Treat Sample

All analyses will be done using the modified intent-to-treat principle (mITT). Under this principle, the evaluable sample will include all randomized participants for whom study treatment was initiated (e.g. attended at least one treatment session), regardless of the treatment actually received. Participants will be analyzed according to the group to which they were randomized. For secondary and exploratory analyses, missing data will not be explicitly imputed.

5.3 Completers Sample

The primary analysis will be repeated using the subset of randomized participants for whom study treatment was initiated (e.g. attended at least one treatment session) and the PNT was collected at 1 week post-treatment. Participants will be analyzed according to the group to which they were randomized.

5.4 Safety Analysis Sample

All randomized participants who receive at least one session of the treatment are included in the safety analyses, regardless of the duration of intervention administered. Patients will be classified according to the treatment group that was actually received.

6. RANDOMIZATION AND BLINDING

The study is to be conducted in a double-blind manner. The subjects, the site investigators, and the clinical staff involved in this study will not know the intervention assignment. Select members of the Data Coordination Unit (DCU) will be partially blinded, i.e., they will know the intervention group assignment as A or B, but not whether the patient receives active tDCS (A-tDCS) or sham (S-tDCS).

The randomization will take place centrally via the Trial Website (WebDCU). Subjects will be randomized 1:1 (A-tDCS: S-tDCS). The objective of subject randomization is to protect the randomness of treatment allocation and to prevent serious imbalances in baseline age, aphasia type, and severity (as measured by the Western Aphasia Battery revised WAB-R). The block urn method (Zhao et al. 2011) and the minimal sufficient balancing method (Zhao et al. 2012) will be used. The computer program developed at the DCU makes the treatment assignment based on the current status of treatment group distribution within each stratum as well as overall balance of treatment assignment.

A “Real-Time” randomization procedure is implemented via the Trial Website on the WebDCU™ System where the clinical center staff enters the baseline (e.g., age, aphasia type, and AQ severity) and eligibility information of a subject prior to enrollment. If the subject’s eligibility status is confirmed, the computer program on the WebDCU™ server will evaluate the treatment arm distribution and generate a treatment assignment based on the randomization scheme.

7. BASELINE INTERVENTION GROUP COMPARABILITY

Summary statistics for the following baseline variables will be compared between treatment groups. At study conclusion the statistical tests for comparison will be two-sample *t*-test or Wilcoxon rank sum test for continuous scale variables and chi-square or exact test for categorical variables.

Baseline Characteristics, Mean (SD); Median (IQR)	Active-tDCS (N=)	Sham-tDCS (N=)	p-value
Age			
Male sex, frequency (%)			
Race, frequency (%)			
White			
Black			
Other			
Hispanic, frequency (%)			
Years of Education			
Stroke Onset to Enrollment (days)			
Aphasia Type, frequency (%)			
WAB-R AQ			
Current use (at randomization), freq (%)			
SSRIs Antidepressants			
Mixed /Atypical SSRIs			
Non- SSRIs Antidepressants			
Anxiolytics/Antipsychotics			
Anticholinergic Agents			
Dementia medications			
Past medical history, frequency (%)			
Chronic Pain			
Average # headaches/month			
Seizures			
Surgery			
Allergies			
Depression			
Diabetes			
Exercise 20 minutes (times/week)			
Exercise prior to stroke (times/week)			
mRS			
NIHSS			
BNT			
ASRS			
PPTT			
PNT correct			
Naming 80			
PHQ-9			
SIS-16			
Hopkins Action Naming Assessment (HANA)			
Content Units (CU)			
Syllable/CU			
Current Occupation			
.....			
.....			

8. PRIMARY ANALYSIS

8.1 Primary Outcome

The primary outcome will be the change in the number of correctly named items on the PNT (absolute change from pre-treatment and immediate post-testing). The PNT is administered twice (and averaged to reduce variability) on two consecutive days immediately before treatment starts and twice after treatment is completed. The change will be computed as the difference in the number of correctly named items between the average of the two pre-treatment assessments to the average of the two post-treatment sessions.

8.2 Statistical Hypotheses

The Primary Hypothesis 1a: A-tDCS over a targeted region coupled with computer-delivered SALT is associated with greater gains in accuracy in naming pictures, compared to sham coupled with the same computer-delivered SALT in post stroke aphasia. To test this hypothesis, we will compare the change in means of outcome measures in the group who received sham versus the group who received tDCS. The primary outcome variable will be change in accuracy of naming untrained items within one week after treatment ends. The null hypothesis is $H_0: \mu_1 = \mu_2$, where μ_1 is the mean change in accuracy of naming untrained items (PNT correct) between baseline and 1 week post-treatment in the A-tDCS group and μ_2 is the mean change in the sham group. The primary analysis will compare change between groups (A-tDCS versus S-tDCS) using multiple regression and will be adjusted for aphasia type (Anomia, Broca, or other type), baseline aphasia severity (AQ), and age. The primary analysis will be performed using both the Completers and Modified Intent-to-treat Samples. If these two analyses are not consistent, then the trial findings will be interpreted with caution.

Sensitivity analyses will be done for the change in accuracy of trained items using the same approach. Naming errors will also be analyzed and categorized as semantic related, semantic unrelated, real words related phonologically, non-words related phonologically, mixed semantic/phonological, abstruse neologisms, and no response. Additional sensitivity analyses will adjust for education and time from stroke onset to time of treatment initiation in addition to the covariates included in the primary model.

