1. Administer the Western Aphasia Battery-Revised (WAB-R): The WAB-R will characterize the participants' overall language impairment through the evaluation of the main clinical aspects of language functioning, including speech content, speech fluency, auditory comprehension, repetition, and naming. The WAB-R allows for the differentiation of these specific language abilities, as well as the classification of aphasia type. The WAB-R also yields a composite score, the Aphasia Quotient, which provides an overall measure of severity, in which lower scores denote more severe aphasia (Kertesz, 2007). Both the AQ and aphasia type will be used to stratify participants for randomization. This randomization will be done using the Web Data Collection Unit (WebDCUTM), developed at Medical University of South Carolina, after data for the participant are entered by the speech-language pathologists. Speech-language pathologists (SLPs) will refer to the manual for explicit instructions regarding administration and scoring procedures. Administration time will range between 30-45 minutes.

Date: March 2, 2021

Principal Investigator: [name], MA

Application Number: IRB00089018

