8.5 Missing Data

For the primary analysis, for participants who do not complete the 1 week post-treatment assessments, the post-treatment value will be imputed using a multiple imputation approach assuming a FCS missing mechanism and missing is at random (MAR).

As a sensitivity analysis with the modified ITT sample, the primary outcome analysis will be repeated using all available follow-up data (without explicit imputation) in a mixed effects model of the change from baseline in naming accuracy adjusted for baseline (with week (1, 5, or 20 weeks post-treatment) as class variable and a REPEATED statement). The model will include the baseline covariates used for the primary analysis as fixed effects.

The statistical model will be a repeated measures model (SAS® MIXED procedure with REPEATED subcommand) assuming a compound symmetry (CS) covariance structure.

```
PROC MIXED;
  CLASS SUBJID ARM VISITNUM TYPE;
  MODEL CHANGE= ARM|VISITNUM WABAQ TYPE AGE;
    REPEATED VISITNUM / TYPE= CS SUBJECT=SUBJID R RCORR;
  LSMEANS ARM*VISITNUM/pdiff CL;
RUN;
```

The least square (adjusted) mean for each treatment group, and the 95% confidence interval for the comparison (active vs. sham) will be presented at 1, 5, 20 weeks post treatment.

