Hypothesis 2b: To address the hypothesis that SSRI use since stroke onset is associated with greater gains with all treatments in the subacute period, independently of depression, we will collapse participants across treatment groups, and compare the primary outcome measures for participants who have continuously taken SSRIs to participants who have not taken SSRIs. If SSRI use enhances plasticity at the subacute stage, it might augment the effect of A-tDCS and naming therapy without tDCS. Participants who have taken SSRIs for only part of the time will not be included in the analysis. The adjusted mean change (95% CI) in naming accuracy on untrained stimuli from baseline to 1 week, 5 weeks, and 20 weeks post-treatment for the SSRI-treated and the SSRI-untreated groups will be estimated using a mixed effects model adjusting for treatment group, baseline naming accuracy, time (with week 1, 5, or 20 as a categorical variable and a random effect for subject), and any baseline subject characteristic found to be statistically significant in the primary or subgroup analyses. We will then evaluate the independent effects of SSRI use, depression (measured at each time point with PHQ-9 score of ≥ 15), and tDCS vs sham on the primary outcome graphically. Although we may not have the power to detect a significant effect of SSRIs, a few studies with similar small numbers have reported significant effects of SSRIs on stroke recovery measured with less sensitive measures such as the mRS. The goal of this exploratory aim is to determine whether or not we need to control for SSRI use in a subsequent clinical trial of A-tDCS in subacute stroke.

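### The primary regression of PNT change leaves out baseline PNT; adding it is a nearly free, probably modest gain in precision for the confirmatory test.

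*SAP*

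**What the plan says.** SAP 8.1 defines the endpoint: "The primary outcome will be the change in the number of correctly named items on the PNT", taken as the mean of two post-treatment tests minus the mean of two pre-treatment tests. SAP 8.2 analyses that change "using multiple regression and will be adjusted for aphasia type (Anomia, Broca, or other type), baseline aphasia severity (AQ), and age", in both the Completers and the modified intent-to-treat samples. Further sensitivity models in SAP 8.2 keep these covariates and add only education and the interval between stroke and the start of treatment, so they too omit baseline PNT.

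Elsewhere in the plan:

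- SAP 6 has the allocation algorithm work "to prevent serious imbalances in baseline age, aphasia type, and severity" on the WAB-R. PNT is not named.
- Protocol 4a (diagnostic testing) describes the WAB-R as covering "speech content, speech fluency, auditory comprehension, repetition, and naming".
- SAP 7 lists the PNT score in the baseline table with a p-value by arm, but does not say what follows if the arms differ.
- SAP 8.5 describes a sensitivity analysis as a "mixed effects model of the change from baseline in naming accuracy adjusted for baseline", but the code beneath it reads "MODEL CHANGE= ARM|VISITNUM WABAQ TYPE AGE", with no baseline PNT term.
- SAP 11, Hypothesis 2b, specifies a model "adjusting for treatment group, baseline naming accuracy, time" and other terms.
- Protocol 7c (covariates) also omits baseline PNT. SAP 2 says the final SAP overrides the protocol.

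**The concern.** A change score fixes the slope of post-treatment on pre-treatment score at 1. If the true slope is lower, because of regression to the mean or because high scorers have little room to improve on a fixed-item test, change still depends on where a participant started. AQ is a composite in which naming is one of five domains, so people with the same AQ can start at different PNT levels. The part of change that depends on starting PNT, beyond AQ, type and age, is left as unexplained variation.

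What is at stake is precision in the only confirmatory comparison, with 20 to 25 participants per arm. Seen from the single realised sample, the same loss appears as sensitivity to a chance arm difference in starting PNT. If the SAP 7 table shows such a difference, any adjustment decided at that stage would be post hoc.

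**Working it through.** **1. The plan's own figure.** Inputs from SAP 8.3: 20 per arm, difference 23, SD of change 22.2, two-sided alpha 0.05, two-group t-test.

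SE = 22.2 × √(2/20) = 7.02 items; noncentrality 23/7.02 = 3.28; df 38. Power by noncentral t = 0.891. The stated 89% reproduces. It is for an unadjusted test, so it never relied on baseline PNT.

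**2. The SAP 8.2 model.** It has six parameters: intercept, arm, two for type, AQ and age. With n = 40, df = 34. Keeping 22.2 as the residual SD, that is, giving AQ, type and age no credit, power = 0.889.

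**3. Adding baseline PNT.** Let r be the size of the partial correlation of change with baseline PNT, given AQ, type and age. The residual SD becomes 22.2 × √(1 − r²) and df = 33. The documents give no r, so it is assumed.

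| r | Variance reduction (r²) | SE (items) | Power for 23 | Equivalent n, 40/(1 − r²) |
|---|---|---|---|---|
| 0 | 0% | 7.02 | 88.9% | 40.0 |
| 0.1 | 1% | 6.99 | 89.2% | 40.4 |
| 0.2 | 4% | 6.88 | 90.1% | 41.7 |
| 0.3 | 9% | 6.70 | 91.5% | 44.0 |
| 0.5 | 25% | 6.08 | 95.6% | 53.3 |

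The r = 0 row shows that the lost degree of freedom costs under 0.1 point of power (0.8892 to 0.8887). At 25 per arm, power is 0.9476 without the term, 0.9493 at r = 0.1 and 0.9635 at r = 0.3.

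**4. Which r is plausible, given that AQ is already in the model?** As an illustration, assume equal pre and post SDs, a pre–post correlation ρ of 0.7 to 0.9, an AQ–PNT correlation a of 0.6 to 0.9, and AQ related to post-treatment PNT only through baseline PNT. Then

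r = (1 − ρ)√(1 − a²) / √[2(1 − ρ) − a²(1 − ρ)²].

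- ρ = 0.7, a = 0.6: 0.24/√0.5676 = 0.32, a variance reduction of about 10%.
- ρ = 0.9, a = 0.9: 0.0436/√0.1919 = 0.10, a variance reduction of about 1%.

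In these scenarios power for 23 rises by about 0.3 to 3 points. This is why 0.1 to 0.3 is used as the working range and 0.5 is treated as optimistic.

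**5. Chance imbalance.** For an arm difference of 0.3 SD in the part of baseline PNT not explained by the other covariates, the shift is 0.3 × r × residual SD. Using 22.2 as an upper limit for that SD:

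- r = 0.1: 0.7 items
- r = 0.3: 2.0 items
- r = 0.5: 3.3 items

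Against the SE of 7.02 these are 0.09, 0.28 and 0.47 of a standard error. The chance of a difference of at least 0.3 SD in either direction is 2 × [1 − Φ(0.3/√(2/n))], which is 0.34 at n = 20 per arm and 0.29 at n = 25.

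**6. A smaller true effect.** If the difference were 15 (illustrative, 20 per arm), power is 54.6% under SAP 8.2, 55.0% with baseline PNT at r = 0.1 and 58.5% at r = 0.3.

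**The case against.** The case for leaving the model alone is substantial. The outcome is a change score, so an additive difference in starting level is already removed, and averaging two pre-tests weakens regression to the mean. AQ and type carry part of the naming information and are used twice, in allocation and in the model. Randomisation keeps the estimate unbiased on average. The power claim does not depend on the missing term. Hypothesis 2b is a weak precedent, because it compares non-randomised SSRI users with non-users, where baseline adjustment deals with confounding. All of this stands. It limits the size of the point but does not remove it, because nothing in the plan accounts for starting PNT beyond AQ, type and age. The SAP 8.5 sensitivity model would help if its code matched its text, but the code has no baseline PNT term.

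A reader might infer more than the documents support:

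- *Any baseline PNT difference passes into the treatment estimate uncontrolled.* It does not. Only the arm difference times the residual slope of change on baseline remains.
- *Lost precision and chance imbalance are two separate harms.* They are one. Chance imbalance in a prognostic variable is part of the sampling variation that the wider standard error already covers.
- *The omission costs the equivalent of a third more participants.* That needs r = 0.5 after adjustment for AQ, which nothing in the documents supports.

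**Conclusion.** The omission is clear from the text. Its consequence is a loss of efficiency, not a flaw in validity: the primary test keeps its type I error, its estimate is unbiased over randomisations, and the 89% figure is correct for the test it describes. It would be wrong to read the point as saying that the result will be biased or the trial underpowered.

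The size is uncertain and probably modest. Over the working range of r the gain is about 0.3 to 2.6 power points at the planned difference, and the imbalance shift is well under a third of a standard error. Both rest on the assumed r and on 22.2 as the residual SD. The latter makes the item shifts upper readings at each r. The gain in power is somewhat larger if the true difference is below 23. The change is worth making because it costs almost nothing, not because the present model is unsound.

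**What to change.** In SAP 8.2, give the covariate list as: *adjusted for baseline PNT correct (mean of the two pre-treatment tests), aphasia type, AQ and age*. Use the same list in the Completers fit, in the modified intent-to-treat fit and in the imputation model, whose variables SAP 8.5 does not list. The mismatch between text and code in the SAP 8.5 mixed model is a separate point, but the two can be settled together.

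The cost is one line of the SAP and one degree of freedom, with no new data. SAP 2 already provides for an update before database lock and before the code is broken. The change should be made then, so that it is prespecified and not prompted by the baseline table.

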No previous studies have directly evaluated the comparative effectiveness of tDCS on augmenting SALT at different time points relative to stroke onset. The timing of treatment may be an extremely important variable in both the duration and the mechanism of effects, as rodent studies and human studies indicate that there is a “sensitive period” during the first month or so after ischemic stroke during which there is increased responsiveness to motor training (Zeiler & Krakauer, 2015). During this time-limited sensitive period, the unique molecular, physiological, and structural milieu allows heightened plasticity through mechanisms that are qualitatively and quantitatively distinct from plasticity mechanisms that are observed in the absence of stroke or after chronic stroke (Krakauer et al., 2012; Zeiler & Krakauer, 2013; Ng et al., 2015). It is only during this period that increasing (Schabitz et al., 2004) or decreasing brain derived neurotrophic factor (BDNF) (Ploughman et al., 2009) e.g., through neuromodulatory therapies like tDCS,

Date: March 2, 2021

Principal Investigator: [name], MA

Application Number: IRB00089018

has been shown to augment or prevent recovery. In humans, this period of plasticity for language recovery may last as long as three months (Lazar et al., 2010). Thus, it is plausible that tDCS would have its greatest effects in the first three months after stroke.

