The randomization will take place centrally via the Trial Website. Subjects will be randomized 1:1 (A-tDCS: S-tDCS), controlling for clinical center, aphasia type, and severity (classified using the Western Aphasia Battery revised: WAB-R). The computer program developed at the DCU makes the treatment assignment based on the current status of treatment group distribution within each stratum as well as overall balance of treatment assignment. The randomization scheme will never be deterministic. The detailed randomization scheme and source codes will be provided in the Randomization Plan document.

A "Real-Time" randomization procedure is implemented via the Trial Website on the WebDCU™

Date: March 2, 2021

Principal Investigator: [name], MA

Application Number: IRB00089018

System where the clinical center staff enters the basic baseline (e.g. aphasia type, and AQ severity) and eligibility information of a subject prior to enrollment. If the subject's eligibility status is confirmed, the computer program on the WebDCU™ server will evaluate the treatment arm distribution and generate a patient number based on the randomization scheme. The SLP enrolling the patient will not see the treatment assignment, only a numeric patient number which is entered into a software package that controls whether the tDCS given is A-tDCS or Sham. In order to mask treatment type (A-tDCS vs. Sham) for both patients as well as the SLPs administering the treatment session (i.e., setting up the tDCS and starting and monitoring the computerized treatment task), we use in-house software/hardware. As previously discussed, this setup allows for switching the tDCS on and off without any involvement from the patient or experimenter. The software is run on a lap-top computer connected to the tDCS stimulator. Treatment type is encoded in the software so that the administrator only needs to enter a patient and session number to start stimulation without knowing whether those specific numbers are associated with A-tDCS or Sham. The unblinded list of randomization codes and treatment assignments will be generated by the DCU and will be uploaded into the software by a software administrator who is not otherwise involved in the study.

d. Justification of why participants will not receive routine care or will have current therapy stopped

Participation in this study will not disrupt any current care or therapy.

e. Justification for inclusion of a placebo or non-treatment group

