The primary analysis will compare change in accuracy of naming untrained items between groups (A-tDCS versus sham) in a two-sample *t*-test for the Intent-to-treat sample. For participants who do not complete the Week 1 post-treatment assessment, the post-treatment value will be imputed using a multiple imputation approach assuming a monotone missing mechanism and missing is at random (MAR). As a sensitivity analysis, the primary outcome analysis will be repeated using all available follow-up data (without explicit imputation) in a mixed effects model of the change from baseline in naming accuracy adjusted for baseline (with Week 1, 5, or 20 as a categorical variable and a random effect for subject). Similar analyses will be done for the change in accuracy of trained items.

If we accept the null hypothesis, then tDCS is considered clearly ineffective (in improving anomia in stroke patients) and will not be considered for further study. If we reject the null hypothesis, we would consider undertaking a Phase III study of tDCS.

Sample Size Determination

We expect to enroll 50 participants over 4 years, and expect 40-45 will complete the study. We predict no difficulty recruiting at least 10-15 participants with aphasia each year after subacute stroke, as the PI has

Date: March 2, 2021

Principal Investigator: [name], MA

Application Number: IRB00089018

recruited an average of 53 aphasic patients due to acute left hemisphere ischemic stroke each year in her previous studies of aphasia recovery. If sample size in each group is 20, (a total sample size of 40), we will have 89% power to detect a difference in means of 23 (the difference between a A-tDCS mean change in accuracy, μ_1 , of 33 and a sham mean change in accuracy, μ_2 , of 10) assuming that the standard deviation of change for both groups is 22.2 using a two group *t*-test with a two-sided alpha of 0.05. These mean changes for tDCS and sham and standard deviation of change are based on the one published sham-controlled study of tDCS combined with SALT in subacute stroke.

Multiplicity

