Since this is a Phase I/II study, the false positive error rate has been relaxed (Schoenfeld, 1980). For a futility design the type I and type II error rates are reversed as compared to a traditional, superiority hypothesis. For the primary analysis, the probability of incorrectly declaring a drug futile is 0.1 (or 10%, type I error is the false negative rate). Given that the active tDCS comes from a distribution with a mean change of the control group (e.g. the treatment is the same as the sham), the probability of incorrectly moving to a Phase III trial is 0.15 (or 15%, type II error is the false positive rate).

For secondary outcomes and safety analyses, no adjustment of Type I error probability will be considered, since they will be treated as exploratory.

Missing Data

Under the ITT principle, all patients who are randomized are included in the analysis. Therefore, missing data, especially in the primary outcome measure, can be problematic. For the primary futility analysis we will impute missing data using multiple imputation (Rubin, 1987) assuming a monotone missing mechanism and missing is at random (MAR). Similar methods will be employed for secondary analyses and secondary outcomes. For safety data (e.g. AEs) no data imputation will be done.

Interim Analysis

No formal interim analyses are planned.

Adjusting for Covariates

The primary analysis will be adjusted for aphasia type, and baseline aphasia severity (AQ), education, time from stroke onset to time of treatment initiation, and number of previous SLP treatment sessions (prior to our study).

Secondary Analyses

In addition to the primary outcome, several secondary analyses will be conducted. We will examine changes in types of naming errors (defined by the PNT) by tDCS treatment group. The Cinderella story will be analyzed by comparing lexical diversity (VOCD) for nouns, verbs and adjectives; number and types of errors; length and patterns of pauses by treatment group. Pre and post comparisons with both non-aphasic and aphasic speakers from the Aphasia Bank database who share a number of demographic features (e.g., type and severity of aphasia, age, etc.) will also be made. We will also evaluate differences between treatment groups in QOL as measured by the Stroke Impact Scale, mRS, Content Units (CU) and syllables/CU in describing the Cookie Theft picture on the NIH Stroke Scale.

At the end of the study, for the interval scale variables, mean change from baseline to immediate

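### Days from stroke onset to treatment start, which the protocol expects to affect the primary outcome, is not balanced at randomisation and not in the SAP's primary model

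*SAP*

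**What the plan says.** SAP 8.2 compares the arms on change in PNT correct by multiple regression, which "will be adjusted for aphasia type (Anomia, Broca, or other type), baseline aphasia severity (AQ), and age". At the end of the same section it places time from onset in a supporting analysis: "Additional sensitivity analyses will adjust for education and time from stroke onset to time of treatment initiation", on top of the primary covariates. The mixed model in SAP 8.5 carries AQ, type and age only. SAP 11 uses time from onset twice more: as an exploratory subgroup split at one month, and in days as a regressor in the Hypothesis 2a models. SAP 7 tabulates days from onset to enrolment by arm.

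Neither randomisation scheme includes it. The protocol (4c, Randomization and Blinding) allocates "controlling for clinical center, aphasia type, and severity". SAP 6 aims "to prevent serious imbalances in baseline age, aphasia type, and severity".

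The protocol is not consistent about the primary model. Section 7c, Adjusting for Covariates, says "The primary analysis will be adjusted for aphasia type, and baseline aphasia severity (AQ), education, time from stroke onset to time of treatment initiation", and adds the number of previous therapy sessions. But the Primary Analyses text in section 2 and the Statistical Analysis text in 7c both say "The primary analysis will compare change in accuracy of naming untrained items between groups (A-tDCS versus sham) in a two-sample" t-test, with no covariates. SAP 2 gives the final SAP precedence over the protocol.

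**The concern.** Eligibility runs up to three months after stroke, and the protocol's Background says that most language recovery falls in the first few months. Hypothesis 2a predicts that a later start lowers the gain on untrained pictures, which is the primary outcome, and the end of the Background repeats that expectation. The plan thus names a variable that it expects to be related to the outcome, collects it, and leaves it out of both the allocation scheme and the model on which the decision rests. The SAP gives no reason for leaving it out.

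With 20 to 25 per arm, the arms can differ by chance in mean days from onset. If time is prognostic, part of that difference appears in the active-minus-sham estimate, and variance that could be explained stays in the residual. The consequence matters because the protocol says that accepting the null ends further study of tDCS for this use. The time-adjusted sensitivity model adds education and time together. The SAP's only rule for disagreement covers the Completers and modified intent-to-treat samples, so it does not say what follows if the time-adjusted result differs from the primary one.

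**Working it through.** **Inputs from the documents.** SAP 8.3: 20 per group, difference 23 (33 against 10), SD of change 22.2, two-sided alpha 0.05, stated power 89%. SAP 4: target of 50 with the one-week PNT, so 25 per arm. Protocol 5: within three months of onset.

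**Assumptions.** The documents give neither a distribution of days from onset nor its correlation with change. I take days as uniform over 0 to 90, and let *r* be the size of the correlation with change. For power, *r* is the partial correlation given AQ, type and age, and 22.2 stands in for the residual SD of the SAP model.

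**1. The plan's own figure.** Noncentral *t*, 38 df, noncentrality 23 / (22.2 × √(2/20)) = 23 / 7.02 = 3.28. Power is 89.1%, so the stated 89% reproduces.

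**2. Size of chance imbalance.** The SD of a uniform over 0 to 90 is 90/√12 = 25.98 days.
- 20 per arm: SE of the difference in means = 25.98 × √(2/20) = 8.22 days; 1.96 × 8.22 = 16.1 days.
- 25 per arm: 25.98 × √(2/25) = 7.35 days; 1.96 × 7.35 = 14.4 days.

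**3. Shift in an estimate not adjusted for time.** Slope = *r* × 22.2 / 25.98, or 0.17 items per day at *r* = 0.2 and 0.38 at *r* = 0.45. Multiplying by the imbalance, the SD of days cancels, so the shift is *k* × *r* × 22.2 × √(2/n) for an imbalance of *k* standard errors.

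| Imbalance | *r* = 0.2 | *r* = 0.45 | Share of 23 |
|---|---|---|---|
| 1 SE, 20 per arm | 1.4 items | 3.2 items | 6–14% |
| 1.96 SE, 20 per arm | 2.8 items | 6.2 items | 12–27% |
| 1.96 SE, 25 per arm | 2.5 items | 5.5 items | 11–24% |

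The shift can go either way. It favours active when the active arm happens to start earlier.

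**4. Power with time in the model.** The residual SD becomes 22.2 × √(1 − r²). The SAP model has 2n − 6 df (intercept, arm, two type terms, AQ, age); adding time leaves 2n − 7. The difference is 23.

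| Partial *r* | 20 per arm | 25 per arm |
|---|---|---|
| Without time | 88.9% | 94.8% |
| 0 | 88.9% | 94.7% |
| 0.2 | 90.1% | 95.5% |
| 0.3 | 91.5% | 96.3% |
| 0.4 | 93.4% | 97.4% |
| 0.5 | 95.6% | 98.5% |

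If time turns out not to be prognostic, the loss is at most about 0.1 point.

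**The case against.** The case for leaving the SAP alone has several parts.

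- *A time-adjusted estimate is already planned.* SAP 8.2 prespecifies it as a sensitivity analysis, SAP 8.4 tests it at 0.05, and Model 1 of Hypothesis 2a regresses one-week change on arm, AQ, age, education and days. An imbalance would also show in the baseline table. This stands, and it limits the harm. It does not change which estimate carries the decision. Model 1 also omits aphasia type.
- *The SAP's covariate set is coherent.* Its three covariates are the three factors that its randomisation balances. That is a defensible rule, but it does not explain leaving out a variable that the plan itself expects to matter.
- *The protocol is a weak precedent.* One section lists time for the primary analysis and two describe a plain t-test. This stands, so the argument should rest on the expected effect of time and not on a breach of the protocol. The protocol's list, "education, time from stroke onset to time of treatment initiation, and number of previous SLP treatment sessions", also contains items that this point does not ask to restore.
- *The size is assumed.* This also stands. The 1.96-SE row is an extreme. Even there the shift is 1.96 × *r* = 0.39 to 0.88 of the treatment difference's own standard error, and such variation is already covered by the confidence interval. To the extent that AQ, type or age correlate with time, the shifts would be smaller.

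A reader might also infer that the documents treat time from onset as the main driver of gain. They do not go that far. Hypothesis 2a is a prediction, the Background says only that timing may matter, and "In humans, this period of plasticity for language recovery may last as long as three months" covers the whole eligibility window. Nothing ranks time above aphasia severity, which is both balanced and adjusted for.

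**Conclusion.** The omission is real and worth correcting, as a matter of precision and protection against chance imbalance. It does not invalidate the primary analysis. A reader might conclude that the primary estimate is biased or unadjusted. Neither follows: randomisation keeps the test valid on average, and the model adjusts for three covariates, lacking only time.

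Under the stated assumptions, an ordinary imbalance moves the estimate by 1.4 to 3.2 items and an extreme one by up to about 6, against 23. The power gain at 20 per arm is roughly 1 to 7 points. Both ranges depend on correlations that the documents do not supply. The facts about what is and is not in the model do not depend on them. The case for the change is that it costs almost nothing if time is irrelevant and helps if the plan's own hypothesis is right.

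**What to change.** In the SAP update that section 2 already foresees before database lock and unblinding:

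1. Add days from stroke onset to first treatment session, as a continuous term, to the primary regression in 8.2 alongside aphasia type, AQ and age.
2. Add the same term to the MODEL statement of the PROC MIXED sensitivity analysis in 8.5, whose text already says that it carries the primary covariates.
3. Keep education in the sensitivity analysis.

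If the sponsor prefers the present model, the SAP should give the reason before unblinding.

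The cost is one degree of freedom and a short edit. The variable is already needed for the planned sensitivity analysis and for Hypothesis 2a. Because treatment is assigned at the start of Visit 3, the first treatment visit, it is in effect a baseline covariate. There is no need to change the randomisation factors, which would be an operational change and not an edit to the SAP, or to extend the covariate to all the outcomes in SAP 10.
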